6.2 Subject Exclusion Criteria

Patients who fulfil any of the following criteria are not eligible for admission to the study:

- Uncontrolled intercurrent illness including active infection requiring systemic therapy or symptomatic congestive heart failure within 6 months
- Has known active central nervous system (CNS) metastases and/or carcinomatous meningitis. Subjects with previously treated brain metastases may participate provided they are stable (without evidence of progression by imaging for at least four weeks prior to the first dose of trial treatment and any neurologic symptoms have returned to baseline), have no evidence of new or enlarging brain metastases, and are not using steroids for at least 7 days prior to trial treatment. This exception does not include carcinomatous meningitis which is excluded regardless of clinical stability.
- Evidence of clinically significant immunosuppression such as the following:
 - Primary immunodeficiency state such as Severe Combined Immunodeficiency Disease
 - Concurrent opportunistic infection

- Receiving systemic immunosuppressive therapy (> 2 weeks) including oral steroid doses > 10 mg/day of prednisone or equivalent within 7 days prior to enrollment. However, in the setting of non-immune mediated indications for use, chronic/active low dose steroid use may be permitted at the discretion of the principal investigator.
- Known history of human immunodeficiency virus (HIV) disease.
- History or evidence of symptomatic autoimmune disease (e.g., pneumonitis, glomerulonephritis, vasculitis, or other), or history of active autoimmune disease that has required systemic treatment (i.e., use of corticosteroids, immunosuppressive drugs or biological agents used for treatment of autoimmune diseases) in past 2 years prior to enrollment. Replacement therapy (e.g., thyroxine for hypothyroidism, insulin for diabetes or physiologic corticosteroid replacement therapy for adrenal or pituitary insufficiency) is not considered a form of systemic treatment for autoimmune disease.
- Active herpetic skin lesions or prior complications of herpetic infection
- Require intermittent or chronic treatment with an intravenous or oral antiherpetic drug (e.g., acyclovir), other than intermittent topical use
- Has known active Hepatitis B (e.g., HBsAg reactive) or Hepatitis C (e.g., HCV RNA [qualitative] is detected).
- Received live vaccine or live-attenuated vaccine within 30 days prior to enrollment.
Note: Seasonal influenza vaccines for injection are generally inactivated flu vaccines and are allowed; however intranasal influenza vaccines (e.g., Flu-Mist®) are live attenuated vaccines, and are not allowed.
- Has a known history of active TB (Bacillus Tuberculosis)
- Female subject is pregnant or breast-feeding, or planning to become pregnant or male subject is planning to father a child within the projected duration of the trial, starting with the pre-screening or screening visit, during study treatment and through 3 months after the last dose of talimogene laherparepvec or 4 months after the last dose of pembrolizumab, whichever is later.
- Male and female subjects of childbearing potential who are unwilling to use acceptable method(s) of effective contraception during study treatment and through 3 months after the last dose of talimogene laherparepvec and 4 months after the last dose of pembrolizumab. (Note: Women not of childbearing potential are defined as: Any female who is post-menopausal [age \geq 55 years with cessation of menses for 12 or more months or less than 55 years but not spontaneous menses for at least 2 years or less than 55 years and spontaneous menses within the past 1 year, but currently amenorrhoeic (e.g., spontaneous or secondary to hysterectomy), and with postmenopausal gonadotropin levels (luteinizing hormone and follicle-stimulating hormone levels > 40 IU/L) or postmenopausal estradiol levels (< 5 ng/dL) or according to the definition of "postmenopausal range" for the laboratory involved] or who have had a hysterectomy, bilateral salpingectomy, or bilateral oophorectomy).
- Sexually active subjects and their partners unwilling to use male or female latex condom or polyurethane condoms for patients with latex allergies to avoid potential viral transmission during sexual contact while on treatment and within 30 days after treatment with talimogene laherparepvec.
- Subject who is unwilling to minimize exposure with his/her blood or other body fluids

to individuals who are at higher risks for HSV-1 induced complications such as immunosuppressed individuals, individuals known to have HIV infection, pregnant women, or children under the age of 1 year, during talimogene laherparepvec treatment and through 30 days after the last dose of talimogene laherparepvec.

- Known previous history of sensitivity to talimogene laherparepvec or any of its components to be administered during dosing (e.g. sorbitol, myo-inositol)
- Hypersensitivity to pembrolizumab or any of its excipients.
- Has a history of (non-infectious) pneumonitis/interstitial lung disease that required steroids or has current pneumonitis/interstitial lung disease.
- Prior therapy with talimogene laherparepvec, tumor vaccine.
- Prior chemotherapy, radiotherapy, biological cancer therapy, targeted small molecule therapy or major surgery within 21 days prior to study Day 1 or who has not recovered (i.e., to CTCAE \leq grade 1 or at baseline) from adverse events due to previously administered therapy. Note: Subjects with \leq grade 2 neuropathy and alopecia are an exception to this criterion and may qualify for the study. Note: If subject received major surgery, they must have recovered adequately from the toxicity and/or complications from the intervention prior to starting therapy.
- Is currently participating and receiving study therapy with another investigational device or study drug or has participated in a study of an investigational agent and received study therapy or used an investigational device within 3 weeks of the first dose of treatment.
- Has known psychiatric or substance abuse disorders that would interfere with cooperation with the requirements of the trial.
- The presence of any other concurrent active malignancy.

7.0 RECRUITMENT PLAN

Both men and women and members of all races and ethnic groups are eligible for this trial. The clinical trial will be listed on the clinicaltrials.gov website and on the websites of participating institutions. Patients will be identified through internal referrals and external referrals by Medical and Surgical Oncologists, nationally and internationally. Patients will be recruited through the Sarcoma Disease Management Team of the Memorial Sloan Kettering Cancer Center. The Sarcoma Service and the Sarcoma Disease Management Team each hold weekly interdepartmental meetings to identify study participants for open clinical trials. We will also discuss the trial and patient recruitment with several Sarcoma patient support groups. The principal investigator will be available to all patients for further questions and information through a contact number, which will be provided on the consent form.

7.1 Research Participant Registration

Confirm eligibility as defined in the section entitled Inclusion/Exclusion Criteria. Obtain informed consent by following procedures defined in section entitled Informed Consent Procedures. During the registration process, registering individuals will be required to complete a protocol-specific Eligibility Checklist. The individual signing the Eligibility Checklist is confirming whether the participant is eligible to enroll in the study. Study staff are responsible for ensuring that all institutional requirements necessary to enroll a participant to the study have been completed.

8.0 Informed Consent Procedures

The consent form/research authorization meets the requirements of the Code of Federal Regulations and the Institutional Review Board/Privacy Board of this Center. The consent form will include the following:

1. The nature, objectives, potential risks, and benefits of the intended study.
2. The length of study, what it entails, and the likely follow-up required.
3. Alternatives to the proposed study. (This will include available standard and investigational therapies. In addition, patients will be offered an option of supportive care for therapeutic studies.)
4. The name of the investigator(s) responsible for the protocol.
5. The right of the participant to accept or refuse study interventions/interactions and to withdraw from participation at any time.
6. How the participants' data will be protected, who will have access to their PHI, and what data will be disclosed for research purposes

Prior to inclusion in the study and before protocol-specified procedures are carried out, the consenting professionals will explain the details of the protocol as outlined in the consent and research authorization to the participants/LARs. The participant/LAR will also be informed that they are free to withdraw from the study at any time. The consent discussion may occur in person or remotely via teleconference, telephone, or videoconference.

All participants/LARs must sign an IRB/PB-approved consent form/research authorization indicating their consent to participate. Each participant/LAR and consenting professional will sign and date the consent form. The participant/LAR must receive a copy of the signed informed consent form.

9.0 PRETREATMENT EVALUATION

Screening

All aspects of the screening evaluation should be completed prior to entering the study, unless otherwise noted:

Within 30 days of study start:

- Confirmation of disease: documented presence of metastatic and/or inoperable, locally advanced sarcoma with at least one palpable lesion deemed suitable for direct intralesional injection of talimogene laherparepvec and at least one target lesion. The palpable lesion may be used as the target lesion for RECIST assessment if it meets the RECIST 1.1 criteria for a target lesion and no other appropriate target lesion exists.
- All patients enrolled in this study will undergo a new baseline biopsy where feasible
- Informed Consent

Within 3 weeks of study start:

- Full medical history, physical exam, assessment of performance status by KPS or ECOG status
- Review of concomitant medications
- Complete vital signs (pulse, blood pressure, temperature, respiratory rate) as well as weight and height. Height may be documented at any time prior to registration.
- Standard baseline imaging with CT scan of the chest (with or without contrast), abdomen and pelvis (with contrast where renal function permits) and MRI if applicable. Additional imaging for research purposes may also be performed where clinically appropriate.
- 12-lead electrocardiogram (EKG)
- Serum β -HCG pregnancy test for women with child-bearing potential. (within 72 hours)
- Complete blood count with differential, including lymphocyte and eosinophil count.
- Comprehensive metabolic panel (glucose, blood urea nitrogen, creatinine, sodium, potassium, chloride, bicarbonate, calcium, total protein, albumin, serum bilirubin, alkaline phosphatase, ASL, AST), phosphorus, magnesium, TSH, T4 free, amylase, lipase.
- Review of inclusion and exclusion criteria

Please refer to Study Calendar in Section 10 for additional information.

9.0 TREATMENT/INTERVENTION PLAN

9.1 Study drugs

Treatment will be administered on an outpatient basis. Reported adverse events and potential risks are described in section 11.0. Modifications and dose delays due to toxicity are described further in section 11.3. The schedule of evaluations and interventions is described in Section 10.

Patients will be treated with up to 4mL at 10^6 pfu/mL of talimogene laherparepvec given on Week 1 and up to 4mL at 10^8 pfu/mL starting at Week 4 every 3 weeks thereafter.

Pembrolizumab at 200mg/dose will be given on Week 1 and every 3 weeks thereafter for up to 35 cycles. Patients will be reassessed at week 8 and then every 8 weeks until week 56 and then every 12 weeks thereafter or as per the discretion of the treating investigator .

Talimogene laherparepvec will be administered by intralesional injection into injectable lesions with or without image ultrasound guidance. The initial dose (Week 1) of talimogene laherparepvec is up to 4.0 mL of 10^6 plaque-forming units (PFU)/mL. Subsequent doses of talimogene laherparepvec are up to 4.0 mL of 10^8 PFU/mL. When talimogene laherparepvec and pembrolizumab are administered on the same day, talimogene laherparepvec must be administered first.

Pembrolizumab at a dose of 200mg will be administered intravenously on Week 1 and every 3 weeks (\pm 3 days). Pembrolizumab infusion should be administered in 30 minutes, with a window of -5 and +10 minutes, using an infusion pump.

No additional investigational or commercial agents or therapies other than those described below may be administered with the intent to treat the patient's malignancy.

9.1.1 Dose rationale

The toxicity profile of talimogene laherparepvec used as single agent based on the same proposed dose was well studied in early phase clinical trials as well as in a large, randomized phase III trial in patients with melanoma.^{51, 49, 50} In a phase 1b/2 trial also in patients with melanoma using the same doses of talimogene laherparepvec in combination with ipilimumab, although Grade 3/4 adverse events occurred in 32% of the patients, only 2 patients had possible immune-related grade 3 or 4 adverse events and no DLTs were reported.⁷¹ In addition, a Phase Ib/II study of the combination of talimogene laherparepvec and pembrolizumab in patients with melanoma has recently completed accrual. In this study, talimogene laherparepvec was administered five weeks prior to initiating pembrolizumab. Patients were given intratumoral talimogene laherparepvec injection at doses up to 4 mL per treatment (10^6 PFU/mL on day 1, then 10^8 PFU/mL on day 22 and every 2 weeks thereafter). Intravenous pembrolizumab was given at a dose of 200mg from Day 36 in phase 1b (n = 20) and Day 1 in phase 2 (n = 90) and then every two weeks thereafter. The combination appeared to be safe and well tolerated.⁹²[2] The FDA has now approved pembrolizumab, administered intravenously at a dose of 2mg/kg every 3 weeks, for the treatment of patients with unresectable and metastatic melanoma. Intralesional injection of talimogene laherparepvec, also known as IMLYRIC®, has been approved by the United States Food and Drug Administration (FDA) for the local treatment of unresectable cutaneous, subcutaneous, and nodal lesions in adult patients with melanoma recurrent after initial surgery. However, it has not been shown to increase OS or have an effect on metastases to internal organs including the liver and lungs.

The suggested treatment plan is summarized in Table 4. Patients will be offered an optional biopsy at the time of progression of disease.

Table 4. Study design and treatment plan

	Talimogene laherparepvec	Pembrolizumab
One stage design based on the exact binomial test	Intratumoral administration (injection): Up to 4mL at 10^6 pfu/mL at Week 1 Up to 4mL at 10^8 pfu/mL at Week 4 and every 3 weeks thereafter.	Dose: 200mg/dose at Week 1, and every 3 weeks thereafter.

Toxicities will be assessed using the NCI CTCAE (version 4.03) unless otherwise specified and discussed in detail in section 11.0.

9.2 Duration of Therapy

In the absence of treatment delays due to adverse events, treatment with intralesional talimogene laherparepvec may continue until one of the following criteria applies:

- Disappearance of injectable lesions
- Complete response
- Confirmed progression of disease (detailed in section 13) or clinical progression
- Intercurrent illness that prevents further administration of treatment
- Intolerance of study treatment (detailed in section 11.1)
- Completion of 35 treatments (approximately 2 years) with pembrolizumab
 - o Note: The number of treatments is calculated starting with the first dose. Participants who stop the combination or pembrolizumab after receiving 35 doses may be eligible for retreatment if they progress after stopping study treatment provided they meet the requirements detailed in Section 9.2.1. Participants may be retreated in the Second Course Phase (Retreatment) for up to an additional 17 cycles (approximately 1 year).
- Patient is lost to follow-up
- Physician's decision to withdraw a patient from the study for a reason not listed
- Patient decides to withdraw from the study
- End of study, whichever occurs first.

In the absence of treatment delays due to adverse events, treatment with pembrolizumab may continue until one of the following criteria applies:

- Confirmed progression of disease (detailed in section 13) or clinical progression
- Intercurrent illness that prevents further administration of treatment
- Intolerance of study treatment (detailed in section 11.1)
- Patient is lost to follow-up
- Completion of 35 treatments (approximately 2 years) with pembrolizumab
 - o Note: The number of treatments is calculated starting with the first dose. Participants who stop the combination or pembrolizumab after receiving 35 doses may be eligible for retreatment if they progress after stopping study treatment provided they meet the requirements detailed in Section 9.2.1. Participants may be retreated in the Second Course Phase (Retreatment) for up to an additional 17 cycles (approximately 1 year).
- Physician's decision to withdraw a patient from the study for a reason not listed
- Subject is lost to follow-up
- Patient decides to withdraw from the study
- End of study, whichever occurs first.

Subjects with a complete response (CR) may stop injections of talimogene laherparepvec, but treatment with pembrolizumab will be continued unless one of the criteria for treatment discontinuation is met. This is discussed in again in section 13.0.

Due to the mechanism of action, subjects may experience growth in existing tumors or the appearance of new tumors prior to maximal clinical benefit of talimogene laherparepvec and pembrolizumab. The patient may be allowed to continue study treatment after initial RECIST 1.1 defined progression if they are assessed by the treating physician to be deriving clinical benefit and tolerating study treatment. The treating physician may consult with the overall study PI for help with assessing the patient. Such patients should discontinue study therapy upon further evidence of progression.

9.2.1 Second Course

All participants in the inoperable, locally advanced/metastatic cohort who stop study treatment with SD or better may be eligible for up to an additional 17 cycles (approximately 1 year) of pembrolizumab and talimogene laherparepvec treatment if they progress after stopping study treatment from the initial treatment phase and have lesions that are eligible for injection as defined in the inclusion criteria. This retreatment is termed the Second Course Phase of this study and is only available if the study remains open and the participant meets the following conditions:

Either

- Stopped initial treatment with study treatment after attaining an investigator-determined confirmed CR based on RECIST 1.1, and
 - Was treated with at least 8 cycles of study treatment before discontinuing treatment, and
 - Received at least 2 treatments with pembrolizumab beyond the date when the initial CR was declared

OR

- Had SD, PR, or CR and stopped study treatment after completion of 35 administrations (approximately 2 years) of study treatment for reasons other than disease progression or intolerance

AND

- Experienced an investigator-determined radiographic disease progression by RECIST 1.1 after stopping initial treatment, and
 - Have at least 1 injectable cutaneous, subcutaneous (superficial or deep) soft tissue or nodal lesion ≥ 10 mm in longest diameter as defined in the inclusion criteria.
 - No new anticancer treatment was administered after the last dose of study treatment, and
 - The participant meets all of the safety parameters listed in the inclusion criteria and none of the safety parameters listed in the exclusion criteria, and

- The study is ongoing

An objective response or disease progression that occurs during the Second Course Phase for a participant will not be counted as an event for the primary analysis of either endpoint in this study.

**Note: patients must have measurable disease at the start of protocol treatment to be eligible for this provision.*

9.3 General Concomitant Medication and Supportive Care Guidelines

Supportive Care: Best supportive care and treatment will be given as appropriate to each subject as per Clinical Center and ASCO guidelines (antiemetics, antibiotics, packed red blood cell and platelet transfusions, nutritional support, non-radiation palliative treatment for pain).

Steroids:

Doses up to 10mg of prednisone daily (or equivalent) will be allowed concurrently with continuous treatment with talimogene laherparepvec and/or pembrolizumab. If the subject requires corticosteroid dosing of >10 mg prednisone daily (or equivalent) and/or other immunosuppressive medication for related toxicities, talimogene laherparepvec and pembrolizumab dosing must be held until the corticosteroid dose has decreased to ≤10 mg prednisone daily (or equivalent) and the administration of the other immunosuppressive medication has discontinued. In the setting of non-immune mediated indications for use, chronic/active low dose steroid use (at doses >10 mg prednisone daily) may be permitted at the discretion of the principal investigator.

Radiation:

Radiation therapy is only allowed during the study if required for palliation of symptoms due to underlying sarcoma.

Surgery:

Subjects must not schedule any elective surgeries during the treatment period and for at least 30 days after the last administration of study drugs. If a subject undergoes any unexpected surgery during the course of the study, all study treatments must be withheld and the investigator or designee should report the event per their institutional guidelines. A subject may be allowed to resume study drugs per PI's discretion.

Other supportive measures and specific treatments/guidelines recommended for the management of toxicities are detailed in Appendix A.

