AE(s)=adverse event(s); ALT= alanine aminotransferase; AST=aspartate aminotransferase; CTCAE=Common Terminology Criteria for Adverse Events; DRESS=Drug Rash with Eosinophilia and Systemic Symptom; GI=gastrointestinal; IO=immuno-oncology; ir=immune related; IV=intravenous; SJS=Stevens-Johnson Syndrome; T1DM=type 1 diabetes mellitus; TEN=Toxic Epidermal Necrolysis; ULN=upper limit of normal.

Note: Non-irAE will be managed as appropriate, following clinical practice recommendations.

^a AST/ALT: >3.0 to 5.0 x ULN if baseline normal; >3.0 to 5.0 x baseline, if baseline abnormal; bilirubin:>1.5 to 3.0 x ULN if baseline normal; >1.5 to 3.0 x baseline if baseline abnormal
^b AST/ALT: >5.0 to 20.0 x ULN, if baseline normal; >5.0 to 20.0 x baseline, if baseline abnormal; bilirubin:>3.0 to 10.0 x ULN if baseline normal; >3.0 to 10.0 x baseline if baseline abnormal
^c AST/ALT: >20.0 x ULN, if baseline normal; >20.0 x baseline, if baseline abnormal; bilirubin: >10.0 x ULN if baseline normal; >10.0 x baseline if baseline abnormal
^d The decision to withhold or permanently discontinue pembrolizumab is at the discretion of the investigator or treating physician. If control achieved or ≤ Grade 2, pembrolizumab may be resumed.
^e Events that require discontinuation include, but are not limited to: encephalitis and other clinically important irAEs (eg, vasculitis and sclerosing cholangitis).

Dosing interruptions are permitted in the case of medical / surgical events or logistical reasons not related to study therapy (e.g., elective surgery, unrelated medical events, patient vacation, and/or holidays). Subjects should be placed back on study therapy within 3 weeks of the scheduled interruption, unless otherwise discussed with the principal investigator. The reason for interruption should be documented in the patient's study record. The patient's treatment schedule should be reset from the date that therapy is reinitiated.

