12.2.1 Disease Parameters

Measurable disease – Measurable lesions are defined as those that can be accurately measured in at least one dimension (longest diameter to be recorded for non-nodal lesions and short axis for nodal lesions) as >20mm by chest x-ray, as >10mm with CT scan or MRI, or >10mm with calipers by clinical exam. All tumor measurements must be recorded in millimeters (or decimal fractions of centimeters).

To be considered pathologically enlarged and measurable, a lymph node must be > 15 mm in short axis when assessed by CT scan (CT scan slice thickness recommended to be no greater than 5 mm). At baseline and in follow-up, only the short axis will be measured and followed.

Note: Tumor lesions that are situated in a previously irradiated area are not considered measurable unless there is evidence of progression after radiation therapy.

Non-measurable disease – All other lesions (or sites of disease), including small lesions (longest diameter <10mm or pathological lymph nodes with ≥ 10 to <15mm short axis) are considered non-measurable disease. Bone lesions, leptomeningeal disease, ascites, pleural/pericardial effusions, lymphangitis cutis/pulmonitis, inflammatory breast disease and abdominal masses (not followed by CT or MRI), are considered as non-measurable.

Target lesions – All measurable lesions up to a maximum of 2 lesions per organ and 5 lesions in total, representative of all involved organs, should be identified as target lesions and recorded and measured at baseline. Target lesions should be selected on the basis of their size (lesions with the longest diameter), be representative of all involved organs, but in addition should be those that lend themselves to reproducible repeated measurements. A sum of the diameters (longest for non-nodal lesions, short axis for nodal lesions) for all target lesions will be calculated and reported as the baseline sum diameters. The baseline sum diameters will be used as a reference to further characterize any objective regression in the measurable dimension of the disease.

Non-target lesions – All other lesions (or sites of disease) including any measurable lesions over and above the 5 target lesions should be identified as non-target lesions and should also be recorded at baseline. Measurements of these lesions are not required, but the presence, absence or in rare cases unequivocal progression of each should be noted throughout follow-up.

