12.3.1.3 Evaluation of Best Response

The best response is the best response recorded from the start of the treatment until disease progression/recurrence (taking as reference for progressive disease the smallest measurements recorded since the treatment started). The patient's best response assignment will depend on the achievement of both measurement and confirmation criteria.

Table 13. Evaluation of Best Response – RECIST criteria

Target Lesions	Non-Target Lesions	New Lesions	Best Response	Best Response for This Category also Requires:
CR	CR	No	CR	≥ 4 wks. Confirmation
CR	Non-CR/Non-PD	No	PR	≥ 4 wks. Confirmation
PR	Non-CR/Non-PD	No	PR	
SD	Non-CR/Non-PD	No	SD	documented at least once ≥ 4 wks. from baseline
PD	Any	Yes or No	PD	no prior SD, PR or CR
Any	PD*	Yes or No	PD	
Any	Any	Yes	PD	

* In exceptional circumstances, unequivocal progression in non-target lesions may be accepted as disease progression.

Note: Patients with a global deterioration of health status requiring discontinuation of treatment without objective evidence of disease progression at that time should be reported as "***symptomatic deterioration***." Every effort should be made to document the objective progression even after discontinuation of treatment.

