12.4.1 Special note on target lesions that become “too small to measure”

While on study, all lesions (nodal and non-nodal) recorded at baseline should have their actual measurements recorded at each subsequent evaluation, even when very small (e.g. 2mm). However, sometimes, lesions or lymph nodes which are recorded as target lesions at baseline become so faint on CT scan that the radiologist may not feel comfortable assigning an exact measure and may report them as being “too small to measure”. When this occurs, it is important that a value be recorded on the D2M form. If it is the opinion of the radiologist that the lesion has likely disappeared, the measurement should be recorded as 0 mm. If the lesion is believed to be present and is faintly seen but too small to measure, a default value of 5 mm should be assigned.

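### No rule says how to score a target lesion irradiated on study, so shrinkage from palliative radiotherapy can count toward CR or PR

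*Combined protocol and SAP*

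**What the plan says.** On local therapy, Section 9.3 reads: "Radiation therapy is only allowed during the study if required for palliation of symptoms due to underlying sarcoma". It sets no limit on which lesion may be irradiated.

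On response:

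- Section 12.4.1 says that lesions recorded at baseline, nodal or not, "should have their actual measurements recorded at each subsequent evaluation, even when very small". A lesion the radiologist judges to have gone is entered as 0 mm.
- Section 12.3.1.1 defines PR as a fall of at least 30% in the target sum from baseline.
- Section 12.3.1.3 sets the window: "The best response is the best response recorded from the start of the treatment until disease progression/recurrence".
- Section 12.4 asks for confirmation at least 4 weeks later.
- Section 12.2.1 has the only response text on irradiated lesions: "Tumor lesions that are situated in a previously irradiated area are not considered measurable unless there is evidence of progression after radiation therapy". It stands as a note to the definition of measurable disease.
- Section 12.10 ends PFS at documented progression, death or the last evaluable assessment.
- Section 12.12 (irRECIST) and Section 14.1 (evaluability, replacement, censoring) do not mention radiotherapy or surgery to a target lesion.

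On surgery, Section 9.3 says "Subjects must not schedule any elective surgeries during the treatment period and for at least 30 days after the last administration of study drugs". Section 11.4.2 gives as accepted reasons for interrupting dosing "e.g., elective surgery, unrelated medical events, patient vacation, and/or holidays".

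**The concern.** Radiotherapy to a target lesion is an intercurrent event for the primary endpoint. It can shrink the lesion that is being measured, and a need for symptom relief does not have to coincide with RECIST progression. The response window can therefore still be open when the lesion shrinks. Nothing in the plan removes the lesion from the sum, makes the assessment not evaluable, fixes response status at the last earlier scan, or calls the patient a non-responder. Confirmation 4 weeks later gives little protection if the local effect lasts.

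The error would favour the study drugs, and a single-arm trial has no comparator to offset it. Patients with few target lesions are the most exposed. Section 9.0 (Pretreatment Evaluation) lets the palpable lesion chosen for injection serve as the target lesion when no other suitable one exists. The irRECIST window can stay open longer, because new lesions are not automatically progression there. Without a written rule, each case is left to individual judgement in an unblinded trial.

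**Working it through.** **Inputs.**

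- Rule: at least 3 responses in 20, with 5% not promising and 30% promising (14.1).
- PR threshold: 30% (12.3.1.1).
- Target lesions: at most 5, and 2 per organ (12.2.1).
- First 20 patients: ORR 35% overall and 30% at 24 weeks, that is 7/20 and 6/20 (4.1).
- Cohort size: 10 (14.1, Table 15).
- Not in the documents: the fraction q of true non-responders whom local therapy would turn into apparent responders. Taken as 1% to 5%, purely as an assumption.

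**1. The plan's own figures.** P(X >= 3) = 1 - sum over x = 0, 1, 2 of C(20,x) p^x (1-p)^(20-x).

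- p = 0.05 gives 0.0755 (printed 0.08).
- p = 0.30 gives 0.9645 (printed 96%).
- Clopper-Pearson limits are 0.025-0.556 for 2/10 and 0.067-0.652 for 3/10, matching Table 15.

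**2. When local shrinkage alone makes a PR.** Let the treated lesion hold share w of the baseline sum and shrink by fraction s, with the other targets unchanged. The sum falls by w x s, and PR needs w x s >= 0.30. With k equal-sized targets, w = 1/k:

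| k | fall if the lesion vanishes | shrinkage needed for PR |
|---|---|---|
| 1 | 100% | 30% |
| 2 | 50% | 60% |
| 3 | 33% | 90% |
| 4 | 25% | not reachable |
| 5 | 20% | not reachable |

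With unequal lesions, take a 60 mm treated target and a 20 mm untreated one: w = 60/80 = 0.75. Shrinkage of 40% gives 0.75 x 0.40 = 30.0%, exactly on the threshold. Shrinkage of 39% gives 29.25% and fails. The route is real when there are one to three targets or one dominant lesion. It is not automatic.

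**3. Effect in a 10-patient cohort.** One false responder adds 1/10, or 10 points. For example, 2/10 (0.03-0.56) becomes 3/10 (0.07-0.65).

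**4. Effect on the first 20.** One false responder adds 1/20, or 5 points. The 24-week result is 6 against a threshold of 3. Removing three leaves 3, which still passes. Removing four leaves 2, which fails.

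**5. Type I error under the assumption.** With p = 0.05 + 0.95q:

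| q | p | P(at least 3 of 20) |
|---|---|---|
| 0 | 0.0500 | 0.0755 |
| 1% | 0.0595 | 0.113 |
| 3% | 0.0785 | 0.204 |
| 5% | 0.0975 | 0.309 |

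This shows how sensitive the rule is. It does not estimate what happened in this trial.

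**The case against.** The strongest reply is that the problem is inferred from silence. No sentence says that an irradiated lesion stays in the sum. Section 12.4.1 is a note about lesions too small to measure. The note in 12.2.1 could be stretched to lesions irradiated on study, and Section 12.1 defers to the published RECIST 1.1 guideline, which is not reproduced. This stands in part: retention follows from 12.3.1.1, 12.3.1.3 and 12.4.1 together with the lack of any exception. The 12.2.1 note, however, sits where lesions are selected at baseline and does not say how to score a target treated later.

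Other limits also stand. The objectives in Section 2.0 fix response at 24 weeks. With scans every 8 weeks and confirmation, a false response needs early radiotherapy, a fall of at least 30% in the whole sum, and no earlier progression. Clinical progression is a reason to stop treatment (9.2), and a need for palliation may often accompany progression. These points make cases fewer but do not say how to score one.

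A reader might infer that elective surgery lets target lesions be resected and scored as 0 mm. Section 11.4.2 does not support this: it lists surgery with vacations among events unrelated to study therapy and never mentions tumour resection. A reader might also see Section 9.3 as contradicting itself on radiotherapy, because its supportive-care list covers only pain palliation without radiation. Radiation has its own paragraph there, so the two can be read as complementary.

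**Conclusion.** The gap is real and bears on the primary endpoint. Applied literally, the response rules can credit radiotherapy shrinkage of a target lesion to T-VEC plus pembrolizumab, under both RECIST 1.1 and irRECIST. Resection is a possible but less likely route. The size per case is firm: 10 ORR points in a cohort of 10 and 5 points in the first 20. The number of cases is unknown.

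A reader might conclude that the first-stage finding is unsafe or that its true type I error is 0.11 to 0.31. Neither is supported. The 6/20 result survives up to three false responders, and the type I figures rest on assumed conversion rates of 1% to 5%. The 10-patient cohorts have no decision rule, so there the harm is to the estimates and their intervals. This should be put right, but it does not overturn the trial's reported result.

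The elective-surgery statements in 9.3 and 11.4.2 do contradict each other. That is a separate wording conflict, not evidence of response bias.

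**What to change.** 1. **Response rule.** Add to 12.3.1.3 and 14.1, for RECIST 1.1 and irRECIST: after a target lesion receives non-protocol local therapy, later assessments cannot establish or upgrade CR or PR. A response already confirmed before that date stands. Otherwise the patient stays in the denominator as a non-responder and is not replaced.
2. **ORR sensitivity analysis.** Score response from the untreated target lesions. A patient with none left remains a non-responder.
3. **PFS.** Leave the 12.10 definition as the primary one. For 24-week PFS, add two sensitivity analyses, one treating local therapy to a target lesion as an event and one censoring at it. Censoring alone would not do: it may be informative, because symptomatic patients may be nearer progression, and it could raise the Kaplan-Meier estimate.
4. **Data.** Record the site and date of each such procedure against the target-lesion list.
5. **Surgery wording.** The sponsor must reconcile 9.3 and 11.4.2 on elective surgery during treatment.

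Cost: a few sentences and one small lesion-level field. The study calendar lists review of concomitant medications but not procedures, so the field may need source review. Section 16.3 describes the study as completed, so the rule would be applied uniformly at analysis. ORR may be slightly lower, and an occasional genuine responder irradiated before confirmation would be scored as a non-responder; the analysis in item 2 shows how much that matters.
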